9.7.3.4.4 Methods of Health Related Quality of Life (HRQoL) Endpoints Analysis

Below is the list of HRQoL assessments and other subjective measures:

- HRQoL questionnaires as measured in Section [9.3.2.4.1](#)
- Acute pain associated with hemophilia, as measured with individual bleeding episodes, using the NRS or the Wong Baker Face Scale in pediatric subjects
- Chronic pain will be assessed based on current standard practice at the centre. Chronic pain, if any, will be assessed at the screening visit, on each annual visit and at the termination visit (as well as any interim visit) by using the NRS or the Wong Baker Face Scale in pediatric subjects
- Physical Activity as measured by the questionnaires detailed in Section [9.3.2.4.3](#).

HRQoL assessments, acute and chronic pain scales, and daily activity level will be summarized by treatment regimen (on-demand, prophylaxis) and by rater (subject or care-giver). If available, changes from baseline to follow-up study visit will be summarized by treatment regimen.

Of note, subjects may outgrow their initial version of the HaemoQoL questionnaire. In this case, changes from baseline will be assessed up to their move a further version of the questionnaire.

9.7.3.4.5 Methods of Health Resource Use Related (HRUR) Endpoints Analysis

All HRUR parameters will be summarized by treatment regimen (on-demand, prophylaxis). If available, changes from baseline to each follow-up study visit will be summarized by treatment regimen.

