9. RESEARCH METHODS

9.1 Study Design

This study is a post-authorization, prospective, uncontrolled, non-interventional, multicenter cohort study. Approximately 80 subjects with congenital hemophilia B will be enrolled. Subjects must be prescribed rFIX (RIXUBIS) by the treating physician before study participation. Data will be collected over a period of 4 years from the time of study enrollment. The treating physician will determine the treatment regimen, as well as the frequency of laboratory, radiological, and clinical assessment according to her/his routine. Data will be collected on routinely scheduled and emergency visits. There is no binding visit schedule, however it is recommended that the subjects have at least annual visits. Available data from these visits shall be transcribed onto the electronic case report forms (e-CRFs).

It is considered standard practice for subjects with hemophilia to maintain a diary either on paper or in an electronic form (e.g. Smart Medication) which captures FIX treatment and disease related data. A subject diary will be provided to each subject to assist with the standardization of data collection as stated in Section 9.4.2. Nevertheless, the completion of the diary is a voluntary effort by the individual subject or subject's legally authorized representative. All bleeding events and their treatment recorded in subject diaries during study participation period will be transcribed onto e-CRFs.

QoL questionnaires will be provided at baseline and on an annual basis to subjects or their legally authorized representatives.

As no hypothesis testing or interval estimation will be applied, the sample size for the study is not based on statistical considerations.

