9.2.6 Screening and Follow-up

The study site is responsible for maintaining an enrollment log that includes all subjects enrolled. Data on recruited subjects are expected to be collected during the routine visits. The data will be prospectively collected at the sites and recorded onto e-CRFs from hospital medical records - the subject diaries will be completed by the subjects at home. Details on the assessments/data to be recorded for screening and follow-up, can be found in [Table 2](#).

Table 1 Schedule of Study Procedures and Assessments^a				
Procedures / Assessments	Screening Visit	Interim Visits^e	Annual Visits	Termination Visit
Informed Consent ^b	X			
Eligibility Criteria	X			
Medical History including Hemophilia treatment history	X			
Rixubis Treatment Regimen	X	X	X	X
Non-drug Therapies	X	X	X	X
Concomitant Medications	X	X	X	X
Physical Examination	X	X	X	X
Vital Signs	X	X	X	X
Joint Evaluation	X	X	X	X
Chronic Pain Assessment	X	X	X	X
Surgical Procedures		X	X	X
Subject Diary	D	R/D	R/D	R
Adverse Events ^c		X	X	X
Hemostatic Effectiveness		X	X	X
Health Resource Use	X	X	X	X
HRQoL Questionnaires	X		X	X
Acute Pain Assessment ^d		X	X	X
Daily Activity Level	X		X	X
End of Study Form				X

^a Standard procedure according to routine clinical practice

^b Occurs at enrollment

^c AEs will be collected whenever they occur. Each AE will be evaluated by the investigator for seriousness (Section 11.1.1.1), severity (Section 11.1.2.1) and causal relationship (Section 11.1.2.2)

^d As part of the diary

^e As needed

Table 2 Clinical Laboratory Assessments				
Procedures / Assessments	Screening Visit	Interim Visits^b	Annual Visits	Termination Visit
Inhibitor to FIX ^a	X	X	X	X
FIX clotting assay ^a	X	X	X	X

^a Standard procedure according to routine clinical practice

^b As needed

The following data will be collected at the screening visit according to routine clinical practice:

- Year of birth
- Gender
- Height
- Weight
- If a pediatric patient: percentile of height growth curve and weight growth curve
- Pulse rate
- Blood pressure
- Medical history
- History of hypertension
- Baseline FIX levels
- Family history of inhibitors.
- History of inhibitor development
 - Date(s) of inhibitor detection
 - Total FIX EDs at time of inhibitor detection
Where the exact numbers of ED is not available, one of the following ranges should be selected: 0, 1-4, 5-20, 21-50, 51-100, 101-150 or >150.
 - FIX product used at the time of inhibitor detection

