9.3.2.4.5 Healthcare resource use

Healthcare resource use in subjects receiving rFIX (RIXUBIS) will be assessed to estimate health-related direct and indirect costs if applicable in the country. Also, additional resources which are available at the hemophilia treatment center and routinely used by the subject will be assessed. Direct medical costs, direct non-medical costs and indirect costs (if applicable and available) will be appraised by the valuation of the following resources:

- number of home care nursing visits
- number of physiotherapy sessions
- number of orthopedic consultations
- number of nutritional guidance and training sport/school counseling sessions
- number of psychological support/counseling sessions
- number of social counseling sessions
- number of social support (e.g. disease communicator/trouble shooter) visits
- number of visits for emergency FIX stock available at center
- number of 24h hotline calls available at center
- number of phone counseling sessions of patients
- number of laboratory diagnostics visits available at center
- number of dental consultations
- number of infectiology (immunological counseling) sessions

- usage of an electronic diary/smart phone application (e.g. Smart Medication)
- financial help for center visits (travel expense reimbursement)
- number of patient education (e.g. injection training) sessions
- number of scheduled and unscheduled visits at the site
- number of ER visits
- number of inpatient hospitalization, length of stay and severity of complication related to hemophilia (excluding planned surgery)
- length of stay in the hospital per inpatient hospital and severity/kind of complication
- number of days the subject cannot follow normal daily routine (e.g. school, work) due to bleeding episodes or their treatment.

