9.7 Data Analysis

9.7.1 Datasets and Analysis Cohorts

The effectiveness analysis will be carried out on the primary and secondary endpoints of the study for the following treatment regimens:

- Standard prophylaxis
- On-demand treatment
- Episodic prophylaxis
- ITI

Effectiveness of switch from on-demand to prophylaxis dataset (ESODTP)

Evaluation of effectiveness (ABR, AJBR) after switch from on-demand regimen to prophylaxis in moderate moderately severe and severe hemophilia B patients.

Safety Analysis Set (SAS)

The SAS will consist of data for all subjects who were enrolled, met all inclusion and none of the exclusion criteria, and received at least 1 infusion of FIX (RIXUBIS). If 2 or more AEs are reported together as a unit, the individual Medical Dictionary for Regulatory Activities (MedDRA) preferred terms will be counted as separate events.

Effectiveness Full Analysis Set (EFAS)

The EFAS will consist of data from all subjects who were enrolled, met all inclusion and none of the exclusion criteria. This dataset will be used for the primary effectiveness analysis for the comparison of annualized bleeding rates (ABR, AJBR) between each independent treatment regimen (i.e., prophylaxis, on-demand).

Calculation of Annualized Bleeding Rates (ABR) and monthly Bleeding Rate (MBR)

The ABR will be calculated as follows: $(\text{total number of bleeding episodes} \div \text{observed treatment period in days}) * 365.25$. The monthly bleeding rates (MBR) will be calculated as follows: $(\text{total number of bleeding episodes} \div \text{observed treatment period in days}) * 30.5$. The treatment period for surgeries will be excluded from the bleed rate calculation.

Bleeding occurring prior to the first prophylactic infusion will not be included in the estimation of bleeding rate. The observation period for the on-demand regimen will commence on the day of enrollment (met all inclusion and none of the exclusion criteria); the period for prophylaxis will commence at the first prophylactic infusion once enrolled (met all inclusion and none of the exclusion criteria).

Minimal Observed Treatment Period to Estimate ABR

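### Resource-use counts are summarised as change from baseline to each visit, with no recall window or time denominator and no binding visit schedule, so the change mixes use with interval length

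*Protocol*

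**What the plan says.** Section 9.7.3.4.5 has two sentences. The first summarises every health resource parameter by on-demand or prophylaxis regimen. The second adds that, where data are available, "changes from baseline to each follow-up study visit will be summarized by treatment regimen".

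The parameters are in section 9.3.2.4.5. Most are counts, for example "number of ER visits" and "number of scheduled and unscheduled visits at the site", together with physiotherapy sessions, hospitalisations and days away from normal routine. None carries a per-year unit or a recall period. A few items are not interval counts: use of an electronic diary or app, travel reimbursement, length of stay per admission and severity of complication.

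On timing, section 9.1 states: "There is no binding visit schedule, however it is recommended that the subjects have at least annual visits". It also states: "Data will be collected on routinely scheduled and emergency visits". In Table 1 (section 9.2.6) the row "Health Resource Use" is marked for the screening, interim, annual and termination visits, and a footnote makes interim visits as needed.

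**The concern.** A count can be interpreted only with the period it covers. Here neither side of the subtraction has a stated period. The screening count has no look-back, and a follow-up count may cover a few months before an interim visit or a year or more between annual visits. The text says each follow-up visit, so interim visits are not excluded.

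Visit timing may also depend on the outcome. Emergency visits supply data, while emergency room attendances and unscheduled site visits are themselves resource items. An event can therefore trigger the visit that ends the interval.

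Resource use is a named secondary objective (section 8.3), and section 9.3.2.4.5 intends to value it as direct and indirect costs, which need a common time base. A per-visit change could show a rise or fall that did not happen, or hide one that did. The by-regimen summaries could differ only because subjects on one regimen are seen at different intervals from those on the other.

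**Working it through.** The protocol gives no rate, window or expected value for resource use, so there is no planned figure to reproduce. The check has two parts.

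**1. How the protocol treats time elsewhere**

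- Bleeds (9.7.1): divided by "observed treatment period in days" and multiplied by 365.25.
- Factor consumption (9.7.3.3): annualised units and annualised weight-adjusted dose.
- Invasive procedures (9.7.3.4.3): per year per subject.
- Joint scores at irregular visits (9.7.3.4.3): interpolated to months 0, 12, 24, 36 and 48.
- Screening look-backs (9.2.6): 12 months for bleeds, up to 12 months before treatment initiation for the prior factor IX product, and 5 years for joint evaluations.
- Resource use (9.3.2.4.5, 9.7.3.4.5): no denominator, no alignment to fixed time points and no look-back.

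**2. Size of the effect (illustration; all inputs are assumptions)**

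Let λ be a subject's constant event rate per year, b the months covered by the baseline count and t the months covered by the follow-up count.

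Expected change in the count = λ × (t − b) / 12

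Expected change in the annualised count = λ − λ = 0

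With λ = 4:

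| Follow-up interval t (months) | b = 12 | b = 3 |
|---|---|---|
| 3 | 4 × (3 − 12)/12 = −3 | 0 |
| 6 | −2 | +1 |
| 12 | 0 | +3 |
| 18 | +2 | +5 |
| 24 | +4 | +7 |

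Use is unchanged in every cell. For λ from 1 to 12 per year with b = 12, the spurious change at 6 months runs from 1 × (6 − 12)/12 = −0.5 to 12 × (6 − 12)/12 = −6.

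*Hidden change.* Suppose use truly halves from 4 to 2 per year, with a 12-month baseline and a 24-month follow-up interval. The follow-up count is 2 × 2 = 4, so the change in counts is 4 − 4 = 0. The annualised change is 4/2 − 4 = −2, which shows the halving.

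*Regimen summaries.* At 4 per year on both regimens with b = 12, 12-month intervals on one regimen give 0 and 6-month intervals on the other give −2. The difference of 2 comes from visit frequency alone.

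*Share of variation due to interval length.* In a simulation of 400,000 subjects with a stable rate (Poisson, or gamma-Poisson with a between-subject coefficient of variation of 0.7), b was 12 months and t uniform on 3 to 18 months:

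| λ per year | Mean change in count | Variance explained by interval length | Mean change, annualised |
|---|---|---|---|
| 1 | −0.13 | about 6% | −0.004 to −0.003 |
| 4 | −0.50 | 19–22% | −0.001 to +0.002 |
| 12 | −1.48 to −1.51 | 37–46% | −0.011 to +0.008 |

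The mean changes agree with the formula: the mean interval is 10.5 months, and λ × (10.5 − 12)/12 gives −0.125, −0.5 and −1.5. After annualising, the mean change is about zero and interval length explains none of the variance.

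**The case against.** The strongest reply is that section 9.7.3.4.5 never says the counts are raw or run since the last visit. Denominators and visit windows for secondary descriptive counts are ordinary SAP content. The SAP is a separate document, not at hand, and could annualise. That much stands: the protocol does not forbid a rate. But it does fix a visit-level change from baseline for all parameters, and for counts that is a poor quantity to estimate. The baseline period is also a data-collection matter. If the e-CRF follows the protocol, no later analysis can recover what period a screening count covers.

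Three stronger readings are tempting, and the documents do not support them.

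- A reader might infer that visits are simply unscheduled. Annual visits are recommended and have their own column in Table 1. Using annual visits only would remove much of the inequality in follow-up intervals, though not the undefined baseline. If the baseline and every interval covered 12 months, the bias would be zero.
- A reader might infer that the change reflects interval length instead of resource use. It reflects both. In the simulation, interval length explains about 6% to 46% of the variance.
- A reader might infer a known bias between regimens, for example because on-demand subjects attend more often. Nothing in the protocol says which regimen is seen more often, and no test between regimens is stated for these endpoints.

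**Conclusion.** The point holds as a weakness of the planned summary for the count-type resource items. As written, the per-visit change compares counts over periods that are undefined at baseline and may be unequal at follow-up, so it can create or hide a change.

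The figures show how large the effect could be and are not estimates for this study. The event rate, the baseline period and the spread of intervals are all assumed, and the sign reverses with the baseline: at 6 months and 4 events per year, the change is −2 with a 12-month baseline and +1 with a 3-month one. No single percentage distortion can be claimed.

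The consequence is limited. The endpoint is secondary and descriptive, change from baseline is planned only if available, and neither the primary endpoint nor the sample size is affected.

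**What to change.** 1. For count-type items, replace the per-visit change by events per observed patient-year, that is, the count divided by the time it covers, summarised by regimen. Total events over total time is preferable to averaging rates from single intervals, because a short interval that ends in an emergency visit gives an unstable rate.
2. State a rule for intervals that span a regimen change, for example leaving them out of the by-regimen summary or splitting the count in proportion to time. Regimen-change dates are collected, but section 9.3.2.4.5 lists totals without event dates, so visit dates alone cannot assign the events.
3. Define a look-back for the screening count, for example 12 months as already used for bleeds in section 9.2.6. Report change from baseline only as follow-up annualised rate minus baseline annualised rate, and only for subjects whose screening count covers that look-back.
4. Keep non-count items (diary or app use, travel reimbursement, length of stay per admission, severity of complication) as plain descriptive summaries.

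The change is cheap but not free. Annualising follow-up needs only visit dates already collected and a change of wording. The look-back needs e-CRF wording, adds some retrospective collection with recall error, and helps only subjects not yet screened.

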9.7.4 Planned Interim Analysis of the Study

Interim analyses and progress reports are planned every 12 months. Regular safety updates are to be scheduled as per the safety review plan.

9.8 Quality Control

9.8.1 Investigator's Responsibility

The investigator will comply with the protocol (which has been approved/given favorable opinion by the competent/health authority and/or EC), and applicable regulatory requirements as described in the Non-interventional Trial Agreement. The investigator is ultimately responsible for the conduct of all aspects of the study at the study site and verifies by signature the integrity of all data transmitted to the responsible party. The term "investigator" as used in this protocol as well as in other study documents, refers to the investigator or authorized study personnel that the investigator has designated to perform certain duties. Sub-investigators or other authorized study personnel are eligible to sign for the investigator, except where the investigator's signature is specifically required.

The investigator will retain study documentation and data (paper and electronic forms) in accordance with applicable regulatory requirements and the document and data retention policy, as described in the Non-interventional Trial Agreement.

9.8.2 Direct Access to Source Data/Documents

The investigator/study site will cooperate and provide direct access to study documents and data, including source documentation for monitoring by the study monitor, audits by the MAH or its representatives, review by the EC, and inspections by applicable regulatory authorities, as described in the Non-interventional Trial Agreement. If contacted by an applicable regulatory authority, the investigator will notify the MAH of contact, cooperate with the authority, provide the MAH with copies of all documents received from the authority, and allow the MAH to comment on any responses, as described in the Non-interventional Trial Agreement.

9.8.3 Training

The study monitor will ensure that the investigator and study site personnel understand all requirements of the protocol and his/her regulatory responsibilities as an investigator. Training may be provided at an investigator's meeting, at the study site, and/or by instruction manuals. In addition, the study monitor will be available for consultation with the investigator and will serve as the liaison between the study site and the MAH.

9.8.4 Monitoring

The study monitor is responsible for ensuring and verifying that each study site conducts the study according to the protocol, standard operating procedures, other written instructions/agreements, and applicable regulatory guidelines/requirements. The investigator will permit the study monitor to visit the study site at appropriate intervals, as described in the Non-interventional Trial Agreement. Monitoring processes specific to the study will be described in the clinical monitoring plan (see Section 14.1).

9.8.5 Auditing

The MAH and/or MAH's representatives may conduct audits to evaluate study conduct and compliance with the protocol, standard operating procedures, other written instructions/agreements, and applicable regulatory guidelines/requirements. The investigator will permit auditors to visit the study site, as described in the Non-interventional Trial Agreement. Auditing processes specific to the study will be described in the clinical quality management plan (see Section 14.1).

9.8.6 Non-Compliance with the Protocol

If monitoring and/or auditing identify serious and/or persistent non-compliance with the protocol, the MAH may terminate the investigator's participation.

9.9 Limitations of the Research Methods

This cohort-based, non-interventional study aims to provide a real-life picture on the use of RIXUBIS in patients with congenital hemophilia B. On the other hand, this study design may reflect issues related to huge differences in treatment approach and dosing, laboratory monitoring and data recording. Nevertheless, findings will have a greater clinical relevance and lower selection bias than other study designs.

9.10 Other Aspects

None.

10. PROTECTION OF HUMAN SUBJECTS

10.1 Compliance Statement

This study will be conducted in accordance with this protocol and applicable national and local requirements for good pharmacovigilance practices.

10.2 Subject Privacy

The investigator will comply with applicable subject privacy regulations/guidance as described in the Non-interventional Trial Agreement.

10.3 Ethics Committee(s) and Regulatory Authorities

Before enrollment of patients into this study, the protocol, informed consent form, any promotional material/advertisements, and any other written information to be provided will be reviewed and approved/given favorable opinion by the EC and applicable regulatory authorities. The EC's composition or a statement that the EC's composition meets applicable regulatory criteria will be documented. The study will commence only upon the MAH's receipt of approval/favorable opinion from the EC and, if required, upon the MAH's notification of applicable regulatory authority(ies) approval.

If the protocol or any other information given to the subject is amended, the revised documents will be reviewed and approved/given favorable opinion by the EC and relevant regulatory authorities, where applicable. The protocol amendment will only be implemented upon the MAH's receipt of approval and, if required, upon the MAH's notification of applicable regulatory authority(ies) approval.

10.4 Informed Consent

Investigators will choose patients for enrollment considering the study eligibility criteria. The investigator will exercise no selectivity so that no bias is introduced from this source.

All patients/ and/or their legally authorized representative must sign an informed consent form before entering into the study according to applicable regulatory requirements. An assent form may be provided and should be signed by patients less than 18 years of age. Before use, the informed consent form will be reviewed by the MAH and approved by the EC and regulatory authority(ies), where applicable, (see Section 10.3). The informed consent form will include a comprehensive explanation of the study without any exculpatory statements, in accordance with the elements required by applicable regulatory requirements. Patients or their legally authorized representative(s) will be allowed sufficient time to consider participation in the study. By signing the informed consent form, patients or their legally authorized representative(s) agree to the use of their data for the study, unless they withdraw voluntarily or are terminated from the study for any reason.

